1. STUDY INFORMATION

Title	Brand-specific influenza vaccine effectiveness in three Nordic countries: estimates for the 2024-2025 season
Protocol version identifier	1
Date of latest version of protocol	14 February 2025
EU PAS Register number	EUPAS1000000481
Medicinal products	InfluvacTetra Vaxigrip Tetra Efluelda Tetra Fluad Tetra Flucelvax Tetra
Marketing authorization holder(s)	Abbott Biologicals Sanofi Pasteur Seqirus
Research question and objectives	To provide timely estimates of brand-specific seasonal influenza vaccine effectiveness against laboratory-confirmed and influenza-related outcomes for the 2024-2025 season.
Country(-ies) of study	Denmark, Finland, and Sweden
Authors	[name]; [name]

4. ABSTRACT

Rationale and background: The Nordic countries, Denmark, Finland, and Sweden, provide a unique setting for the study of influenza vaccine effectiveness (IVE). The ubiquitous nationwide demographic and health registers, including vaccination and surveillance data, allow for large study cohorts with near real-time data availability. Seasonal influenza remains a major public health concern, particularly for vulnerable populations such as older adults and individuals at high-risk of serious influenza outcomes. While vaccination is the primary prevention strategy, its effectiveness varies across seasons, virus subtypes, and populations. Data on timely brand-specific IVE are limited.

Research question and objectives: The aim of this project is to evaluate the brand-specific effectiveness of seasonal influenza vaccines in preventing laboratory-confirmed and influenza-related outcomes during the 2024-2025 season in key target populations in Denmark, Finland, and Sweden.

Study objective:

- To provide timely estimates of brand-specific seasonal IVE against laboratory-confirmed and influenza-related outcomes for the 2024-2025 season.

Study design: Nationwide register-based cohort analyses in Denmark, Finland, and Sweden, during the study period from 1 October 2024 until the latest available date in 2025 at time of analyses (e.g., 1 March 2025). We will employ a matched cohort design, utilizing national registers to capture vaccination status, influenza outcomes, and relevant covariates. The study will focus on individuals aged 65 years and older, and adults at high risk of adverse influenza outcomes. IVE will be estimated against laboratory-confirmed influenza, influenza-like illness, hospitalization, ICU admission, and mortality.

Population: Within Denmark, Finland, and Sweden, we will include all individuals aged 65 years and above, and adults at high risk below 65 years of age, who are known residents.

Variables: The primary outcomes are laboratory-confirmed influenza (types A and B, combined and separately), influenza hospitalization, and influenza-related death. The secondary outcomes are hospitalisation for influenza-like-illness, hospitalisation for respiratory infections, ICU admission, and all cause-mortality. Covariates include demographic characteristics and comorbidities.

Data sources: Nationwide demography- and healthcare registers within each participating country.

Study size: We expect to include at least 3.2 million individuals who are included in the key target groups for seasonal influenza vaccination across the 3 Nordic countries. All available data within

countries will be used and the statistical power of our proposed study will be reflected in the 95% CIs of the effectiveness estimates.

Data analysis: Using target trial emulation, vaccinated and unvaccinated cohorts will be compared in matched (1:1) survival analyses to estimate IVE while adjusting for potential confounders. The start of follow-up for matched pairs will be defined as day 14 after vaccination to ensure full immunisation. Sensitivity analyses will include use of negative control outcomes, regression discontinuity analysis, adjustments for prior event rates, and a test-negative case-control design on Danish data (negative test results are currently only available in Denmark).

The findings are aimed at informing regulatory decision-making and vaccination strategies ahead of the 2025-2026 influenza season.

5. AMENDMENTS AND UPDATES

Number	Date	Section	Amendment or update	Reason
1	14.2.2025	9.6 Data management	Added a brief description of the used Common Data Model.	To enhance clarity
2	14.2.2025	9.8 Supplementary analyses and quality control	Added more information on methodological concerns and supplementary analyses.	To provide better overview of the section

6. MILESTONES

Milestone	Planned dates
Project start	1 November 2024
Study planning meeting	15 November 2024
Study Protocol submission to EMA	3 February 2025
Registration in the HMA-EMA Catalogues of real-world data studies	24 February 2025
Study Report submission to EMA	2 May 2025
Manuscript(s) ready for submission to EMA	2 June 2025

7. RATIONALE AND BACKGROUND

Seasonal influenza remains a major public health concern, with a disproportionate impact on older adults aged 65 years and above and individuals who are at increased risk of severe complications, hospitalizations, and mortality associated with influenza infections. Vaccination continues to be the cornerstone of influenza prevention strategies. However, approaches to generate robust estimates of the effectiveness of influenza vaccines has been a subject of extensive research and debate (1).

Several studies have demonstrated moderate effectiveness of seasonal influenza vaccination in elderly populations. Meta-analyses have shown that influenza vaccination is moderately effective against laboratory-confirmed influenza in elderly people during epidemic seasons (2,3). A comprehensive individual participant data meta-analysis by Darvishian et al. examined the effectiveness of seasonal influenza vaccination in community-dwelling elderly people (3). The analysis included 4975 individuals (1829 cases and 3146 controls) from test-negative case-control studies. The researchers observed that influenza vaccination was moderately effective against laboratory-confirmed influenza in elderly people during epidemic seasons when the vaccine matched the circulating type, with a pooled vaccine effectiveness (VE) of 47% (95% CI: 6-70%). Notably, vaccine mismatch or a non-epidemic season was not associated with protection. Significant reductions in influenza-related hospitalizations and mortality have been observed in vaccinated elderly populations (2,4,5). Talbot et al. conducted a prospective observational study over three influenza seasons (2006-2009) to assess the effectiveness of influenza vaccination in preventing hospitalizations in community-dwelling older adults (4). The study included 39 cases and 378 controls. The researchers observed that influenza vaccination was associated with an effectiveness of 61.2% (95% CI: 17.5-81.8%) against laboratory-confirmed influenza hospitalization in adults aged 50 years and older.

The effectiveness of influenza vaccines in high-risk groups is understudied. These populations are at increased risk of severe influenza-related complications, and at the same time their immune systems produce weaker responses to vaccination. A recent study on the effectiveness of 2023 Southern Hemisphere influenza vaccines across eight countries (Argentina, Australia, Brazil, Chile, New Zealand, Paraguay, Thailand, and Uruguay) estimated a pooled vaccine effectiveness of 56.6% (46.2-67.1) against SARI hospitalization among children and adults aged 5-64 years with underlying health conditions. Country-specific estimates varied, ranging from 59.3% (45.9-69.4) in Australia to 28.2% (-44.9 to 64.4) in New Zealand.(6) In immunosuppressed cancer patients, vaccination was associated with lower mortality and reduced risk of influenza-related complications (7), and in RCTs including COPD patients, vaccination was associated with fewer exacerbations (8). In a prospective US evaluation during 2012-16, VE against any influenza was lower among patients with high-risk conditions (41%) than those without (48%; P-for-interaction = 0.02) (9).

VE will vary across different influenza virus subtypes (10,11). A meta-analysis reported pooled VE estimates among older adults of 24% for H3N2, 63% for type B and 62% for H1N1pdm09 (10). In a more recent multi-site evaluation, VE estimates ranged from 26 to 46% against H1N1pdm09, from 2 to 44% against H3N2 and from 50 to 85% against type B. For older adults, VE estimates ranged from 28 to 37% against H1N1pdm09, from 28 to 42% against H3N2 and from 58 to 66% against type B (11).

The moderate effectiveness in the elderly, in part due to the impact of immunosenescence (12), has necessitated the development of more immunogenic vaccine formulations in the form of high-dose vaccines, adjuvanted vaccines and recombinant vaccines. Studies have shown promising results for these enhanced vaccines. For instance, MF59-adjuvanted trivalent inactivated vaccines (MF59-TIV) have demonstrated higher effectiveness in preventing influenza-related hospitalizations and complications compared to non-adjuvanted vaccines in elderly populations (13). Immunosuppressed patients could also benefit from more immunogenic formulations. In an immunosuppressed population, high dose influenza vaccine was more immunogenic than standard dose influenza vaccine against A/H1N1 subtypes but not against H3N2 and B subtypes (14).

The Nordic countries are well-suited to contribute significantly to continuous observational research on influenza VE in target groups. These countries offer unique advantages for conducting such studies due to their comprehensive national health registers, high-quality healthcare systems, and the ability to link various databases using personal identification numbers. In Denmark, a nationwide test-negative case-control study by Emborg et al. utilized Danish health registers to assess the effectiveness of influenza vaccination in individuals aged 65 years and older in the 2015/16 season (15). This study reported VE estimates against H1N1pdm09 of 35.0% (95% CI, 11.1-52.4) and against type B of 4.1% (95% CI: -22.0-24.7). A Finnish-Swedish study by Hergens et al. also used nationwide registers to evaluate the effectiveness of influenza vaccination against laboratory-confirmed influenza in individuals aged 65 years and older during the 2016-2017 season (16). This cohort study included 1,034 and 5,845 cases from Stockholm and Finland, respectively. VEs of 24% (95% CI, 11-35) and 33% (95% CI, 28-38) was reported from Stockholm and Finland, respectively (16).

Despite reassuring observations of moderate effectiveness, especially when the vaccine matches the type and subtype of the circulating influenza virus, some researchers have questioned the universal recommendation of influenza vaccination for populations such as the elderly, calling for more robust study designs, better quality evidence, and the development of more effective vaccines (1,17). It has been argued that many studies, particularly observational ones, have suffered from significant methodological flaws (18). These include selection bias, where healthier individuals are more likely to be vaccinated, and the use of non-specific outcomes like all-cause mortality, which can overestimate vaccine benefits.

The continued evaluation of influenza VE remains important for public health and regulatory decision-making. Despite the widespread use of influenza vaccines, the variability in VE across populations and seasons, virus subtypes, and geographic areas underscores the need for ongoing assessment. This will allow accurate and up-to-date VE data to inform prevention strategies and cost-effectiveness

evaluations, allowing for more efficient allocation of healthcare resources in national immunization programs. Furthermore, seasonal VE studies contribute to the infrastructure and methodologies needed for rapid effectiveness evaluations during potential pandemic situations. By maintaining a robust system for evaluating influenza VE in the European region, the broader goals of public health preparedness and regulatory excellence are also supported. As influenza viruses continue to evolve and use of recent vaccine development platforms such as mRNA-based will increase, continuous assessment of seasonal influenza VE will remain an indispensable tool in the efforts to mitigate the impact of seasonal influenza on vulnerable populations and the national healthcare systems.

8. RESEARCH QUESTION AND OBJECTIVES

We will conduct a large Nordic cohort study combining data from Denmark, Finland, and Sweden to evaluate the brand-specific influenza vaccine effectiveness in preventing influenza outcomes among recommended target groups during the 2024-2025 season (October – April).

Our primary objective is:

- To provide timely estimates of brand-specific seasonal influenza vaccine effectiveness against laboratory-confirmed and influenza-related outcomes for the 2024-2025 season.

The findings are aimed at informing regulatory decision-making and vaccination strategies ahead of the 2025-2026 influenza season.

9. RESEARCH METHODS

9.1 Study design

We will take advantage of the unique nationwide register-data available to us, and construct country-specific cohorts with individual-level information on dates of vaccination and dates of effectiveness endpoints together with relevant covariate information. All Nordic residents are assigned a unique personal identifier at birth or immigration, enabling linkage between register data. Nordic countries have universal and tax-financed healthcare systems and reporting to national registers is mandatory, providing near-complete follow-up of all residents over time.

The study period will start on 1st October 2024 in the three countries. This study start date corresponds to the start of the seasonal influenza vaccination program in the three countries. The study period will end on the last date of data availability at time of analyses during spring 2025.

The study design will build on our previous work with Covid-19 vaccination effectiveness in the Nordic countries (19,20). We will utilize a cohort design in a target trial emulation (TTE) framework to estimate both relative and absolute effects. The evaluations in 65+-yr-olds and risk groups 18-64-yr-olds will be designed as two separate target trial emulations. Key components of the specification and emulation of the pragmatic target trials of the effectiveness of brand-specific seasonal IVE using Nordic nationwide register data are included below in Table 1.

Table 1. Target trial emulation framework

Protocol	Target Trial Specification	Target Trial Emulation
Eligibility criteria	
 • Individuals 65+-years-of-age (trial 1) • Individuals in risk groups 18-64-yr-of-age (trial 2) • Have a permanent residency in Denmark, Finland, or Sweden at start of study period 	Same as for the target trials.
Treatment strategies	Vaccination with any of the following influenza vaccines InfluvacTetra, VaxigripTetra, FludTetra, FluarixTetra or Efluelda Tetra, October 1, 2024 to January 31, 2025 vs vaccination with placebo in the same period.	Same as for the target trials except vaccination with placebo is replaced by no vaccination with any of the vaccines under study.
Treatment assignment	Randomization: Eligible individuals are randomly assigned to receive influenza vaccination with a randomly chosen vaccine brand or no vaccination 1:1	Matching: Eligible individuals who are vaccinated in each country during the study period will be matched 1:1 with individuals who have not yet received a vaccine by age (5-yr bins), sex, region of residence, and presence of comorbidities. Unvaccinated individuals are assigned the index date (date of vaccination) of the matched vaccine recipient.
Outcomes	
Primary:
 
 • Hosp. due to Influenza – Lab. conf + J09-J11 • Lab. conf. Influenza A and B (combined and separately) • Death with influenza – Lab. conf within 30 days before date of death 
Secondary:
 
 • Hosp. due to ILI – J09-J11 • Hosp. due to ARI or SARI – J09-J22 • Hosp. due to Influenza with ICU admission • All-cause mortality 	Same as for the target trials.
Follow-up	Day 14 after date of vaccination or placebo will serve as the start of follow-up until the day of an outcome event, death, emigration or end of influenza season. Controls are censored if vaccinated.	Day 14 (time zero) after date of vaccination in each matched pair (index date) will serve as the start of follow-up until the day of an outcome event, death, emigration or end of influenza season (or latest possible date of data availability). Pairs are

		censored if controls are vaccinated.
Causal contrast of interest	
 • Intention to Treat – average effect of treatment assignment in trial population • Per-Protocol Effect – average effect among those who complied with their assigned treatment. 	
 • Modified Per- Protocol Effect – average effect among vaccinated (“do those who get the seasonal influenza vaccination benefit?”)
Statistical analysis	VE estimated as 1 - Risk Ratio at week 18 since index date using cumulative incidences from the Aalen-Johansen estimator.	Same as for the target trial. Week 18 subject to change according to data availability. Change will be made before any effectiveness results are estimated.

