9.5 Study size

Below we describe key target group sizes, vaccination coverage and recorded influenza infection incidences in the three Nordic countries for the 2023-2024 season. This provides a good indication of the possible study size for the 2024-2025 season. We expect to include at least 3.2 million individuals who are included in the key target groups for seasonal influenza vaccination across the 3 Nordic countries.

In Denmark, the total population of individuals aged 65 years and older, along with the population at increased risk below 65 years of age, consisted of 1,211 million and 554,780 individuals, respectively, as of 20 December 2024. (39) From 1 October 2024 to 20 December 2024, influenza vaccination coverage in these target groups was 75.6% and 29.2%, respectively. (39) As of 13 January 2025, there were 700 confirmed cases of influenza, including 414 hospitalisations, in older adults above 65 years. (40)

In Finland, the total population of individuals aged 65 years and older was 1,315 million with a vaccine coverage of 61% during the 2023-2024 season. The population at increased risk aged between 18 and 64 years comprised of 0,52 million individuals. The influenza A incidence was 65.5 per 10,000 person-years, and influenza A hospitalisation incidence was 5.4 per 100,000 person-years. As of 20 January 2025, there were 3224 confirmed cases of influenza in the Finnish population, including 81 hospitalisations due to influenza in adults aged 65 years and above. (41,42)

In Sweden, the total population of elderly 65 years and above in the four regions under study comprise of 280,000 individuals, with national influenza vaccination coverage of 69% in the 2023/2024 season. (43)

We will utilize all available data to us from the countries' nationwide registers (Denmark and Finland), and regional data sources (Sweden). The statistical power of our proposed study will be reflected in the 95% CI of the effectiveness estimates. We expect to have robust statistical precision for the most widely used influenza vaccine brands within the current season. (44,45)

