9.7 Data analysis

Procedures

We will use a matched cohort design to evaluate the effectiveness of seasonal influenza vaccine in comparison with not receiving a seasonal influenza vaccine. Individuals who have received the vaccine will be matched on the day of vaccination with individuals who have not yet received the vaccine. Individuals will be matched on age (5-year bins), sex, region of residence, and selected comorbidities. The day the seasonal vaccine dose was administered within each matched pair will serve as the index date for both individuals. If individuals who were included as a matched non-vaccinated individual

(i.e., a reference individual) receive a vaccine later than the assigned index date, the pair will be right-censored on the day the non-vaccinated individual is vaccinated. In these cases, the non-vaccinated individuals will be allowed to potentially re-enter as vaccine recipients in a new matched pair on that given date.

Statistical analysis

We will follow individuals from day 14 after the index date (to ensure full immunisation) up until the day of an outcome event, death, emigration, or end of the study, whichever occurs first. Additionally, we will censor individuals with a positive PCR test for influenza in our follow-up period 14 and 30 days after the test (as a positive test will be part of the outcome definitions) for the influenza hospitalisation and death outcome analyses, respectively. We will right-censor matched pairs when the reference unvaccinated individual receives a vaccine during follow-up. Cumulative incidences will be estimated by the Aalen-Johansen estimator, and from these we will calculate the comparative VE as $1 - \text{risk ratio}$ at the start of week 18 (depending on data availability) since index date. The corresponding 95% CI will be calculated using the delta method. Country-specific estimates will be combined by random-effects meta-analyses implemented using the *mixmeta* package in R.

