Quality control will be conducted indirectly to evaluate the validity of our main analyses by 1) making sure that the prevalence of the vaccination schedule and the number of study endpoints match national surveillance dashboards and reports, 2) descriptive and analytical results are compatible with our previous findings, and 3) using a Common Data Model (CDM), by which national register data are standardized to a common structure, format and terminology in order to allow the same statistical programming scripts to be used in each country. The use of a CDM with common statistical programming scripts will facilitate efficient use of resources and reproducibility of the statistical analyses. We will ensure the scientific quality of the work, by division of review tasks (including statistical code review) and responsibilities in a timely fashion and by adhering to the ENCePP Code of Conduct. We will perform matching quality diagnostics to assess the control of matched parameters.

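### In the 65+ trial, unweighted pair censoring moves the in-season risk set away from the vaccinees' mix, so overall absolute effects do not target the stated effect among the vaccinated

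*Protocol*

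**What the plan says.** Section 9.1, Table 1, gives the emulated contrast as a modified per-protocol effect, the "average effect among vaccinated". The text above the table promises both relative and absolute effects, and section 12 lists cumulative incidence curves among the main results.

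Vaccinees are "matched 1:1 with individuals who have not yet received a vaccine by age (5-yr bins), sex, region of residence, and presence of comorbidities". Under section 9.7, if the control is later vaccinated, "the pair will be right-censored on the day the non-vaccinated individual is vaccinated". The statistical analysis paragraph repeats the rule: "We will right-censor matched pairs when the reference unvaccinated individual receives a vaccine during follow-up". Such controls may come back as vaccinees: "the non-vaccinated individuals will be allowed to potentially re-enter as vaccine recipients in a new matched pair on that given date". Whether one person may serve as control for several vaccinees is not stated.

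On estimation, "Cumulative incidences will be estimated by the Aalen-Johansen estimator", and VE is 1 minus the risk ratio at about week 18. Section 9.5 says of the Danish 65+ and under-65 risk groups that "influenza vaccination coverage in these target groups was 75.6% and 29.2%, respectively". It gives 61% for Finnish 65+ and 69% nationally for Sweden, both for 2023-2024. As a check, section 9.8 offers: "We will perform matching quality diagnostics to assess the control of matched parameters".

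**The concern.** A pair contributes in-season follow-up only while its control stays unvaccinated. Where coverage in a matching stratum is high, most pairs are gone before the wave; where it is low, most remain. Censoring therefore depends on the matching variables, which also predict risk. An unweighted curve treats it as independent and gives in-season hazards the stratum weights of the surviving pairs, not of the vaccinees.

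This is separate from unmeasured health differences between vaccinees and controls, and it would persist if matching removed all confounding. The planned diagnostics would not reveal it, because exactly matched variables stay balanced within pairs however the overall mix moves. At stake is whether the absolute benefit reported for regulators describes people who get vaccinated or a population closer to those who do not.

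**Working it through.** The protocol gives no figure to reproduce here.

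**Inputs.** From section 9.5: Danish 65+ population 1.211 million; coverage 75.6% (Denmark), 61% (Finland), 69% (Sweden) and 29.2% (Danish risk group under 65). From section 7: VE 48% without and 41% with high-risk conditions, in one US evaluation. Assumed, because the protocol gives no values: coverage and risk by stratum, uptake mostly in October-November, and a wave peaking about 20 January.

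**1. How many pairs can last.** If each control is used once, at most (1 - c)/c of vaccinees keep a pair once uptake is complete.
- Denmark: 0.244/0.756 = 0.323. That is 1,211,000 x 0.244 = about 295,000 lasting pairs for 1,211,000 x 0.756 = about 916,000 vaccinees.
- Sweden: 0.31/0.69 = 0.449.
- Finland: 0.39/0.61 = 0.639.

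Under random 1:1 matching to not-yet-vaccinated people, every never-vaccinated person in a stratum is used once coverage passes 1 - 1/e, about 63%. Surviving pairs per vaccinee are then 0.32 at 75.6%, 0.45 at 69%, 0.60 at 61% and 0.84 at 29.2%. With reuse of controls the first two become 0.46 and 0.53.

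**2. What happens to the mix.** Take two strata holding 55% and 45% of the 65+ population, with coverage 68% and 85% and control risks of 4 and 12 per 1000 (assumed).
- Overall coverage: 0.55 x 0.68 + 0.45 x 0.85 = 0.374 + 0.3825 = 0.7565.
- Low-risk share of vaccinees: 0.374/0.7565 = 0.494.
- Low-risk share of the never-vaccinated, and so of surviving pairs: (0.55 x 0.32)/(0.55 x 0.32 + 0.45 x 0.15) = 0.176/0.2435 = 0.723. With reuse, the matching calculation gives 0.61.

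**3. Absolute risk.** Control risk with the vaccinees' mix: 0.494 x 4 + 0.506 x 12 = 8.05 per 1000. With the surviving pairs' mix: 0.723 x 4 + 0.277 x 12 = 6.22. Ratio 0.77. With reuse: 0.61 x 4 + 0.39 x 12 = 7.12, ratio 0.88.

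A day-by-day calculation with follow-up from day 14 to week 18 and VE 40% throughout agrees:

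| 65+ scenario | Risk difference, plan / true effect among vaccinated |
|---|---|
| Coverage 75.6% in both strata | 1.00 |
| 73% / 79% | 0.92 |
| 68% / 85% | 0.78 (2.38 v 3.07 per 1000) |
| 68% / 85%, controls reused | 0.88 |
| Highest-risk stratum least vaccinated (72% / 82% / 66%) | 1.15 |

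Other runs with different assumed gradients put control incidence 16-30% too low with single use and 3-15% too low with reuse.

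**4. Relative effect.** Both pair members leave together, so with equal VE in all strata the plan returns 40.0% against a true 40.0%. With 48% in the low-risk and 41% in the high-risk stratum:
- Vaccinees' mix: (0.494 x 4 x 48 + 0.506 x 12 x 41)/8.05 = 42.7%.
- Surviving pairs' mix: (0.723 x 4 x 48 + 0.277 x 12 x 41)/6.22 = 44.3%.

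The shift of about 1.5 points is for this coarse example with single use and every event after the drift is complete. Other runs with the same contrast gave about 0.3 to 1.3 points.

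**5. Trial 2.** At 29.2% overall coverage (22% / 38% by stratum, assumed), the low-risk share is 41% of vaccinees and 44% of surviving pairs. The risk-difference ratio is 0.99.

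**The case against.** The strongest reply has four parts.

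First, the main measure is 1 minus the risk ratio, which joint censoring leaves alone when VE is homogeneous. This stands. Section 7 supports one contrast by risk condition (48% v 41%) and gives no VE gradient by age within 65+. A reader might infer a shift of four points or so, but that needs VE to fall from about 50% to 30% across strata, which the protocol does not support.

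Second, the direction is not settled. A reader might infer that absolute effects are always understated. Section 9.8 says people with comorbidities are vaccinated more, but also that the frailest elderly are vaccinated less. Frailty is not a matching variable, yet if the oldest bins follow that pattern the error reverses. No coverage by age bin or comorbidity count is given. This stands too: the direction must be conditional.

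Third, the objective is brand-specific. Table 3 assigns Danish InfluvacTetra and Vaxigrip Tetra to ages 65-69, a single 5-year bin, so age drift there is essentially nil, although comorbidity drift can remain. Danish Fluad Tetra (70+) and Finnish Vaxigrip Tetra (all target groups) still span several bins. The cap of 32% of Danish vaccinees also holds only if each control is used once, which the protocol does not say.

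Fourth, weighting might be left to an analysis plan, and sections 9.3 and 12 already plan stratification and baseline tables before and after matching. This answers less. The protocol itself fixes the contrast, the matching, the censoring rule and the estimator, and these do not fit together as written. Stratified results narrow the drift within strata but leave the overall brand estimate as it is. The baseline tables show vaccinees lost at matching, not pairs lost later.

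**Conclusion.** The point holds for trial 1 and for absolute measures. At 61-76% coverage, the overall cumulative incidences and risk differences refer to a population between the vaccinees and the never-vaccinated, at or near the latter where coverage is high and controls are used once. They match Table 1's target only if coverage is flat across matching strata.

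The sizes rest on assumed stratum coverages, risks, and uptake and season curves. With uptake rising with risk (supported by section 9.8 for comorbidity, an assumption for age), absolute effects are understated by roughly 10-30% with single use of controls and about 5-15% with reuse. With the highest-risk strata less vaccinated they are overstated, by 15% in the example. The consequence for VE is small. The documents do not support extending the point to trial 2, where the error is about 1%.

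**What to change.** For trial 1, estimate the Aalen-Johansen curves within strata of age bin by comorbidity count, collapsing sparse strata, and standardise both arms to the mix of all eligible recipients of that brand. Alternatively, weight pairs for censoring on the matching variables. If a brand or outcome has too few events for either, keep the unweighted estimate and restate the population it refers to. State whether controls may be reused, since this changes the size of the drift.

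In all cases, report the share of recipients still in a pair at the start of circulation and at week 18, with their age and comorbidity mix beside that of all recipients.

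The data are already held. The cost is a small change to the common script, some collapsed strata and somewhat wider intervals.
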